7.6.1 Overall Adverse Events

Adverse events will be classified by primary System Organ Class (SOC) and Preferred Term (PT) according to the latest version of the Medical Dictionary for Regulatory Activities (MedDRA) in production at BMS at the time of database lock.

AEs and SAEs with an onset on or after the start of study therapy through 30 days after the last dose of study therapy will be considered as occurring during study therapy. These will be summarized and presented by SOC and PT both in descending order of frequency over all treatment arms, unless otherwise specified.

Table 7.6.1-1: Adverse Event Summaries

Endpoint	During Study Therapy	During Study Therapy, after Switch to Continuation Dose
SAEs	X	X
SAEs leading to death ^a	X	
SAEs related to study therapy and leading to death ^a	X	
Non-SAEs ≥ 5% ^a	X	
AEs leading to discontinuation of study therapy	X	X
AEs - All Grades	X	
AEs - Grade 2 to 4	X	
AEs- Grade 3 to 4	X	

Table 7.6.1-1: Adverse Event Summaries

Endpoint	During Study Therapy	During Study Therapy, after Switch to Continuation Dose
Related AEs - All Grades	X	
Related AEs - Grade 2 to 4	X	
Related AEs - Grade 3 to 4	X	
CDC Class C AIDS Events	X	
Events of Special Interest	X	
Exposure-adjusted Events $\geq 5\%$	X	
Exposure-adjusted SAEs ^a	X	
Exposure-adjusted SAEs related to study therapy ^a	X	
Exposure-adjusted non-SAEs $\geq 5\%$ ^a	X	

a ClinicalTrials.gov or EudraCT reporting requirement

7.6.2 Deaths

All deaths recorded on the status page, the AE page or SAE page of the CRF will be considered in the analyses. A listing of all deaths that occur will be produced for the enrolled subjects.

7.6.3 Serious Adverse Events

SAEs occurring during study therapy will be summarized by SOC and PT. SAEs leading to death and SAEs related to study therapy and leading to death will be summarized in a similar way.

A listing of all SAEs will be produced, displaying all SAEs (including pre-treatment events) for enrolled subjects.

7.6.4 Serious Adverse Events Emerging After Switch to Continuation Therapy

For subjects who switched to a continuation dose after Week 24, rather than starting on a continuation dose at the time of randomization, SAEs with an onset after the start date of continuation therapy through 30 days after the last dose of study therapy, will be summarized by SOC and PT.

7.6.5 Non-Serious Adverse Events

Non-serious adverse events occurring in at least 5% of the subjects treated will be summarized by SOC and PT.

7.6.6 Adverse Events Leading to Discontinuation of Therapy

Adverse events leading to discontinuation will be summarized by SOC and PT.

7.6.7 Adverse Events Leading to Discontinuation of Therapy After Switch to Continuation Therapy

For subjects who switched to a continuation dose after Week 24, rather than starting on a continuation dose at the time of randomization, AEs leading to discontinuation with an onset after the start date of continuation therapy will be summarized by SOC and PT.

7.6.8 Adverse Events by Relationship

Drug-related adverse events are those with ‘related’ or missing relationship to study drug. Drug-related adverse events will be summarized by SOC and PT.

7.6.9 Adverse Events by Intensity

Adverse events and drug-related adverse events with the following grades:

- all Grades,
- Grade 2 to Grade 4,
- Grade 3 to Grade 4,

will be summarized by SOC and PT.

Adverse events with missing intensity are included only in the summaries for all grades. If a subject has an adverse event with different intensities over time, then only the greatest intensity will be presented.

7.6.10 CDC Class C AIDS Events

CDC Class C AIDS events will be summarized and presented by SOC and PT.

7.6.11 Adverse Events of Special Interest

Separate summaries will be provided for the following events of special interest: gastrointestinal events. The list of events will be identified before database lock. The definition of gastrointestinal events will be based on existing Standardized MedDRA Queries (SMQs) if existing SMQs support the events of special interest requirements. If needed, a customized SMQ (cSMQ) will be developed. Gastrointestinal events will be summarized by SOC and PT.

7.6.12 Multiple Adverse Events

Several descriptive summaries of adverse events that take into account the number of occurrences that an AE was reported by individual subjects will be provided. In order to prepare these summaries, the CRF data will be processed according to standard BMS algorithms to categorize each line of subject data as a new occurrence or a continuation of an existing event.

This determination will be based upon onset and resolution dates. Each line of subject data will represent the maximum severity observed as well as the last known assessed relationship to study medication by the investigator.

This data will be presented as the rate per 100 years of patient exposure. Exposure to study medication will be calculated according to approved standard BMS algorithms as well.

As an example, if 5 subjects report 7 unique episodes of headache and had a combined cumulative exposure of 20 years to study medication, the incidence rate is reported as $7 / 20 * 100$ or 35 cases per 100 patient years of exposure.

For adverse events with multiple occurrences, the following will be provided:

- A table showing the total number and rate (exposure adjusted) of occurrences for general AEs occurring in at least 5% of the subjects treated.
- A listing displaying the unique instances of all AEs (i.e., after duplicates have been eliminated and overlapping and contiguous occurrences of the same event have been collapsed).

Exposure-adjusted summaries will also be provided for SAEs, SAEs related to study therapy and non-SAEs.

7.6.13 Clinical Laboratory Evaluations

Laboratory parameters will be presented using SI and US values and units.

7.6.13.1 Laboratory Abnormalities

The incidence of laboratory abnormalities presenting the worst toxicity grade during the treatment period will be tabulated by treatment arm for all grades (Grades 1, 2, 3, 4) and Grades 3 and 4.

Subjects with at least 1 measurement after the start of study therapy will be included in the summaries. Abnormalities are determined from laboratory measurements analyzed at the central or local laboratory. Grading categories for laboratory tests are determined using the DAIDS grading system (see Appendix 3 of the protocol).

This incidence will be further summarized by baseline toxicity grade.

Treatment emergent abnormalities by toxicity grade (increased to Grades 1, 2, 3, 4, and any grade) will also be summarized by baseline toxicity grade (normal, Grade 1 to 4, not reported) and total analogously. Treatment emergent abnormalities are those with a higher on-treatment toxicity grade than the baseline toxicity grade (including not reported baseline).

7.6.13.2 Laboratory Tests over Time

All summaries of laboratory data over time will use observed values. Visit windows are defined in [Section 8](#).

Observed values and changes from baseline in creatinine and creatinine clearance will be summarized at each scheduled visit by treatment arm.

Observed values, changes from baseline and percent changes from baseline will be summarized over time for the following laboratory tests:

- Fasting Total cholesterol,
- Fasting HDL-cholesterol
- Fasting LDL-cholesterol,
- Fasting Triglycerides.
- Total:HDL cholesterol ratio

Values obtained after the start of serum lipid-reducing agents will be excluded from these lipid summaries. Mean percent changes from baseline using observed values will be plotted at each scheduled visit with error bars representing 1 standard error of the reported statistic.

7.6.14 Electrocardiograms

QRS, PR and QTc Fridericia intervals and changes from baseline will be summarized over time by treatment arm using observed values. Standard 95% confidence intervals for mean changes from baseline will also be provided.

The subject's longest interval observed during the treatment period for these ECG parameters will be summarized categorically by treatment arm using the following categories:

- QRS interval: < 100, 100 to < 110, 110 to < 120, 120 to < 130, 130 to < 140, ≥ 140 msec;
- PR interval: < 200, 200 to < 220, 220 to < 240, 240 to < 260, 260 to < 280, 280 to < 300, ≥ 300 msec;
- QTcF interval: < 400, 400 to < 425, 425 to < 450, 450 to < 460, 460 to < 470, 470 to < 480, 480 to < 490, ≥ 490 msec.

The largest change from baseline in these intervals observed during the treatment period is also summarized categorically by treatment arm using the following categories:

- Δ QRS: < 0, 0 to < 10, 10 to < 20, 20 to < 30, 30 to < 40, ≥ 40 msec;
- Δ PR: < 0, 0 to < 20, 20 to < 40, 40 to < 60, 60 to < 80, ≥ 80 msec;
- Δ QTcF: < 0, 0 to < 10, 10 to < 20, 20 to < 30, 30 to < 40, ≥ 40 msec.

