3.34	Summary Statistics for Fasting Lipid Values and Percent Change from Baseline - US Units Modified Treated Subjects	Table S.7.2.1F / rt-zl-pchglipidss1.lst / SS_VL_T_006
3.35	Summary Statistics for Renal Biomarker Values and Change from Baseline - US Units Modified Treated Subjects	Table S.7.5.1A / rt-zl-bmrenals1.lst / SS_VL_T_006
3.36	Summary Statistics for Renal Biomarker Values and Change from Baseline - SI Units Modified Treated Subjects	Table S.7.5.1B / rt-lb-bmrenals1.lst / SS_VL_T_006
3.37	Summary Statistics for Renal Biomarker Values and Percent Change from Baseline - US Units Modified Treated Subjects	Table S.7.5.1C / rt-zl-pchbmrenals1.lst / SS_VL_T_006

CONFIDENTIAL

AI468038/205891

Number	Title	BMS Table number/File Name/BMS Template
3.38	Summary Statistics for Renal Biomarker Values and Percent Change from Baseline - SI Units Modified Treated Subjects	Table S.7.5.1D / rt-lb-pchbmrenals1.lst / SS_VL_T_006
3.39	Summary Statistics for Bone Biomarker Values and Change from Baseline - US Units Modified Treated Subjects	Table S.7.5.1E / rt-zl-bmbones1.lst / SS_VL_T_006
3.40	Summary Statistics for Bone Biomarker Values and Change from Baseline - SI Units Modified Treated Subjects	Table S.7.5.1F / rt-lb-bmbones1.lst / SS_VL_T_006
3.41	Summary Statistics for Bone Biomarker Values and Percent Change from Baseline - US Units Modified Treated Subjects	Table S.7.5.1G / rt-zl-pchbmbones1.lst / SS_VL_T_006
3.42	Summary Statistics for Bone Biomarker Values and Percent Change from Baseline - SI Units Modified Treated Subjects	Table S.7.5.1H / rt-lb-pchbmbones1.lst / SS_VL_T_006
3.43	Summary of Electrocardiogram Values and Changes from Baseline over Time Modified Treated Subjects	Appendix 7.3.1A / rt-eg-sumchgs1.lst / SS_EG_T_003
3.44	Summary of Electrocardiogram Change from Baseline Category Modified Treated Subjects	Appendix 7.3.1B / rt-eg-changecats1.lst / SS_EG_T_001
3.35	Summary of Electrocardiogram Category Modified Treated Subjects	Appendix 7.3.1C / rt-eg-cats1.lst / SS_EG_T_002

Number	Title	BMS Table number/File Name/BMS Template
3.46	Summary of Vital Sign Values and Changes from Baseline over Time Modified Treated Subjects	Appendix 7.4.1A / rt-vs-sums1.lst / SS_VL_T_006

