3 GENERAL CRITERIA/CONVENTIONS

3.1 Exceptions to Global and/or Departmental Standards

Location of Documentation	Standards Document	Exception
https://external.bms.com/teams/GBS-bms955176/genprogdocs/Forms/AllItems.aspx	Demographics Domain Requirements Specification	Standards Request #8246: Add countries within geographic regions to Template GS_DM_T_X_002 and GS_DM_T_T_002. Add 2 columns "Geographic Region" and "Country" to end of Template GS_DM_L_X_001.
https://external.bms.com/teams/GBS-bms955176/genprogdocs/Forms/AllItems.aspx	Laboratory Test Results (SI Units) (US Units) Domain Requirements Specifications, Physical Measurements Domain Requirements Specifications, Vital Signs Domain Requirements Specifications	Standards Request #8247, #8251, #8255: Display N, mean, SD, median, IQR for values and changes from baseline over time, with the option to specify absolute or percent changes (see Template SS_VL_T_006).
https://external.bms.com/teams/GBS-bms955176/genprogdocs/Forms/AllItems.aspx	Laboratory Test Results (SI Units) (US Units) Domain Requirements Specifications	Standards Request #8252: Display select lab tests in side-by-side columns in all lab listings, similar to GS_LB_L_S_007, not just LFTs (see Template SS_LB_L_001).
https://external.bms.com/teams/GBS-bms955176/genprogdocs/Forms/AllItems.aspx	Electrocardiogram Domain Requirements Specification	Standards Request #8248: Modify Template GS_EG_T_X_005 to replace min and max with median, Q1, Q3, and add 95% CI for mean change from baseline (see Template SS_EG_T_003).
https://external.bms.com/teams/GBS-bms955176/genprogdocs/Forms/AllItems.aspx	Laboratory Test Results (SI Units) (US Units) Domain Requirements Specifications	Standards Request #8253: Display select toxicities (eg, Grade 1-4) by baseline tox grade categories (all, normal, Grade 1, 2, 3, 4, not reported) with multiple treatment group columns on the same page (see Template SS_LB_T_001).
https://external.bms.com/teams/GBS-bms955176/genprogdocs/Forms/AllItems.aspx	Laboratory Test Results (SI Units) (US Units) Domain Requirements Specifications	Standards Request #8254: Display treatment emergent lab abnormalities (increased to grade 1, increased to grade 2, increased to grade 3, increased to grade 4, increased to any grade) by baseline tox grade categories (all, normal, Grade 1 to 4, not reported) (see Template SS_LB_T_002).

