20 to <30	11 (22.0)	9 (18.4)	7 (13.7)	10 (20.0)	7 (13.7)
30 to <40	6 (12.0)	2 (4.1)	4 (7.8)	1 (2.0)	5 (9.8)
>=40	1 (2.0)	3 (6.1)	5 (9.8)	3 (6.0)	1 (2.0)
NOT REPORTED	2 (4.0)	0	0	2 (4.0)	1 (2.0)

Parameter	Values
Template ID	SS_EG_T_001
Output File Name	rt-eg-change cats1.lst
Purpose	WK24S1, WK48S1, WK96S1, WK96S2
Table No.	Appendix 7.3.1B
Title 1	Electrocardiogram Change from Baseline Category Summary

Title 2	Treated Subjects - Stage 1
Footnote 1	Each subject is counted only once using the longest change observed.

Parameter	Values
Template ID	SS_EG_T_001
Output File Name	rt-eg-change cats2.lst
Purpose	WK24S2, WK48S2, WK96S2
Table No.	Appendix 7.3.2B
Title 1	Electrocardiogram Change from Baseline Category Summary
Title 2	Treated Subjects - Stage 2
Footnote 1	Each subject is counted only once using the longest change observed.

Template SS_EG_T_002: ECG Category Summary

ECG Parameter (unit) Category (%)	BMS-663068 400 mg BID/ RAL/TDF N = 50	BMS-663068 800 mg BID/ RAL/TDF N = 49	BMS-663068 600 mg QD/ RAL/TDF N = 51	BMS-663068 1200 mg QD/ RAL/TDF N = 50	ATV/r/ RAL/TDF N = 51
PR INTERVAL (MSEC)					
<200	44 (88.0)	46 (93.9)	46 (90.2)	43 (86.0)	49 (96.1)
200 to <220	4 (8.0)	1 (2.0)	5 (9.8)	5 (10.0)	1 (2.0)
220 to <240	0	2 (4.1)	0	0	0
240 to <260	0	0	0	0	0
260 to <280	0	0	0	0	0
280 to <300	0	0	0	0	0
>=300	0	0	0	0	0
NOT REPORTED	2 (4.0)	0	0	2 (4.0)	1 (2.0)
QRS (MSEC)					
<100	39 (78.0)	40 (81.6)	38 (74.5)	38 (76.0)	33 (64.7)
100 to <110	8 (16.0)	8 (16.3)	12 (23.5)	5 (10.0)	12 (23.5)
110 to <120	1 (2.0)	1 (2.0)	1 (2.0)	5 (10.0)	5 (9.8)
120 to <130	0	0	0	0	0
130 to <140	0	0	0	0	0
>=140	0	0	0	0	0
NOT REPORTED	2 (4.0)	0	0	2 (4.0)	1 (2.0)
QTC [FRIDERICIA] (MSEC)					
<400	1 (2.0)	4 (8.2)	2 (3.9)	2 (4.0)	8 (15.7)
400 to <425	17 (34.0)	14 (28.6)	25 (49.0)	29 (58.0)	21 (41.2)
425 to <450	27 (54.0)	25 (51.0)	17 (33.3)	13 (26.0)	16 (31.4)
450 to <460	3 (6.0)	1 (2.0)	5 (9.8)	2 (4.0)	3 (5.9)
460 to <470	0	5 (10.2)	0	1 (2.0)	2 (3.9)
470 to <480	0	0	0	0	0
480 to <490	0	0	1 (2.0)	0	0
>=490	0	0	1 (2.0)	1 (2.0)	0
NOT REPORTED	2 (4.0)	0	0	2 (4.0)	1 (2.0)

Parameter	Values
Template ID	SS_EG_T_002
Output File Name	rt-eg-cats1.lst

Purpose	WK24S1, WK48S1, WK96S1, WK96S2
Table No.	Appendix 7.3.1C
Title 1	Electrocardiogram Category Summary
Title 2	Treated Subjects - Stage 1
Footnote 1	Each subject is counted only once using the longest interval observed.

Parameter	Values
Template ID	SS_EG_T_002
Output File Name	rt-eg-cats2.lst
Purpose	WK24S2, WK48S2, WK96S2

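### The top QTcF categories (change of 40 msec or more, interval of 490 msec or more) leave no final by-arm ECG table that separates values just over those limits from values far above them

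*SAP*

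**What the plan says.** SAP section 7.6.14 (Electrocardiograms) plans two worst-case categorical summaries by arm, one of the longest interval on treatment and one of the largest change from baseline. For QTcF the change bins are "Δ QTcF: < 0, 0 to < 10, 10 to < 20, 20 to < 30, 30 to < 40, ≥ 40 msec", and the interval bins finish with "470 to < 480, 480 to < 490, ≥ 490 msec".

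The templates in section 4.6.8 of the data presentation plan carry the same bins. Under SS_EG_T_001 (change), "Each subject is counted only once using the longest change observed". Under SS_EG_T_002 (interval), "Each subject is counted only once using the longest interval observed".

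The continuous ECG summary uses SS_EG_T_003. Section 3.1 of the data presentation plan records how it departs from the standard: "Modify Template GS_EG_T_X_005 to replace min and max with median, Q1, Q3, and add 95% CI for mean change from baseline".

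The final-analysis appendix, section 3.3.1, keeps all three displays. Table 3.43 is the continuous summary, Table 3.44 is the "Summary of Electrocardiogram Change from Baseline Category Modified Treated Subjects", and the next entry is the "Summary of Electrocardiogram Category Modified Treated Subjects". That last table is printed as 3.35, although it stands between 3.44 and 3.46. Section 3.3.2 keeps a subject-level ECG listing as Listing 25.

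**The concern.** The two categorical tables exist to show the largest ECG effect in each subject, arm by arm. Their value lies in the upper rows, and the upper row for QTcF pools everything from the last cut upward. Two arms could show the same percentage at 40 msec or more while one holds rises just over the line and the other holds much larger ones. If no other summary table shows the tail, a reader of the final safety tables cannot see that difference between arms.

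The change bins also look borrowed rather than chosen. QTcF is the longest of the three intervals on the SAP's own scale, yet it has the same change range as QRS, the shortest, while the PR bins run to 80 msec.

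**Working it through.** There is no planned figure to reproduce. The check is whether any final ECG table resolves QTcF above the last cut.

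**1. Bins in SAP section 7.6.14, side by side (msec)**

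| Parameter | Last interval bin | Change bins: step, last bin |
|---|---|---|
| QRS | 140 or more | 10, then 40 or more |
| PR | 300 or more | 20, then 80 or more |
| QTcF | 490 or more | 10, then 40 or more |

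The QTcF change bins are identical to the QRS bins. The QTcF interval bins are finer near the top: 10-msec steps from 450 to below 490.

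**2. Do the two categorical tables together recover the tail?** Only in part. For one subject with a fixed baseline, longest interval = baseline + largest change. Take two illustrative subjects:

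- baseline 450, rise 42: interval 450 + 42 = 492;
- baseline 400, rise 110: interval 400 + 110 = 510.

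Both fall in the top change bin and both in the top interval bin, so neither table separates them. A rise of 42 from 400 gives 442, which the interval table would place in its 425 to below 450 row. The interval table therefore separates some pairs, but the two tables are not cross-tabulated, so change and interval cannot be matched within a subject.

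**3. Does the continuous table recover it?** SS_EG_T_003 shows N, mean, SD, Q1, median and Q3, with a 95% confidence interval for the mean change, by visit. It has no maximum. With the planned 40 subjects per arm, about 40 × 0.25 = 10 lie above Q3, so the quartiles say nothing about the top few.

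**4. Does the listing recover it?** The Listing 25 shell (GS_EG_L_X_001) is grouped by treatment and gives heart rate, PR, QRS, QT and QTC by subject and visit. It has no change-from-baseline column, so each change must be worked out by hand. It covers Treated Subjects, whereas the tables cover Modified Treated Subjects, which leave out the GCP non-compliant site. To match a table, the reader must also remove those subjects.

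**5. How many subjects might be affected?** The counts printed in the two categorical shells are:

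- change of 40 msec or more: 1 + 3 + 5 + 3 + 1 = 13 of 50 + 49 + 51 + 50 + 51 = 251, or 5.2%;
- interval of 490 msec or more: 0 + 0 + 1 + 1 + 0 = 2 of 251, or 0.8%.

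The column headings name BMS-663068 with raltegravir and TDF. These are mock figures from a different compound and backbone. They show only that such bins need not be empty.

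**The case against.** The strongest reply is that nothing here is wrong. The bins are fixed in advance, the shells match the SAP, and the SAP nowhere defines a moderate or an extreme prolongation. Any table of an unbounded measure must end in an open bin, and a split at a higher cut only moves the open end upward. Subjects far above the limits are still counted in the top row. Exact values are in Listing 25, grouped by arm, and the number of subjects to look up is likely to be small. Arms were planned at about 40 in an estimation study that the sponsor ended early and is reporting in simplified form. The only events of special interest named are gastrointestinal.

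Most of this stands. It rules out calling the bins an error, and it limits the weight of the point. It does not show that any by-arm table resolves the tail.

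A reader might also infer more than the documents support:

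- **That extreme values would be lost or hidden.** They would not be: the listing holds them and the top row counts them.
- **That about 2 of 40 subjects per arm would land in the top change bin**, by applying the shells' 5.2%. That rate belongs to another compound and predicts nothing for this trial.
- **That the interval table is equally weak.** It loses detail only from 490 msec upward.

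**Conclusion.** The point holds as a limit of the summary tables. No final by-arm ECG table separates QTcF changes just over 40 msec, or intervals just over 490 msec, from values far above. The change table is the weaker of the two. The removal of the maximum from the continuous template closes the other route by which a table could have shown the tail.

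The size cannot be put as an expected number of subjects, because the documents give no QTcF data or assumption for this trial. No estimate, decision rule or efficacy conclusion depends on these bins. The change is worth making because it costs almost nothing and improves a safety display. The conclusion rests on no outside threshold: it needs only the bins, the templates and the final display list. Where to place a higher cut is an assumption.

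**What to change.** In SAP section 7.6.14 and in templates SS_EG_T_001 and SS_EG_T_002, split the top QTcF category at a pre-stated higher cut. One option is:

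- change: 40 to below 60, and 60 msec or more;
- interval: 490 to below 500, and 500 msec or more.

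State 60 and 500 msec as assumptions; another cut fixed in advance would also serve. The last bin stays open, but it then isolates the largest values. Carry the split into Table 3.44 and the ECG category table of the final analysis.

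Optionally, restore the maximum in SS_EG_T_003. That would show each arm's largest value at each visit, but not how many subjects lie in the tail, so it complements the split and does not replace it.

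The cost is one extra row in each of two existing tables, possibly sparse, with no new data.

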7.6.15 Vital Signs

All summaries of vital signs over time will use observed values. Visit windows are defined in [Section 8](#). Observed values and changes from baseline will be summarized over time. For blood pressure and heart rate, only sitting assessments will be included in the summaries.

Observed values and changes from baseline for body weight and BMI will be summarized over time.

7.7 Clinical Biomarker Assessments

Renal and bone biomarkers values, changes from baseline and percent changes from baseline will be summarized over time using observed values. Visit windows are defined in [Section 8](#).

The renal biomarkers include urinary beta-2-microglobulin/creatinine and fractional excretion of phosphorous (FeP), defined as

- $100 * [(urine\ phos\ x\ serum\ creatinine) / (serum\ phos\ x\ urine\ creatinine)]$

The bone biomarkers include: N-terminal Propeptide of Type 1 procollagen (P1NP) and Cross-linked C-telopeptide of Type 1 collagen (CTX).

The median change from baseline in FeP over time will be plotted with error bars representing IQR. The median percent change from baseline in P1NP, CTx and urinary beta-2-microglobulin/creatinine over time will be plotted in a similar way.

